10.1 Sample size calculation

Recruitment of 80 participants with a drop-out rate of 10% will be sufficient to give 80% power at the 5% level assuming either an annualised exacerbation frequency 2 or 2.5 per year in the placebo group to observe a 50% or 40% reduction in exacerbation frequency in those receiving anti-ST2 respectively.

This sample size estimate is based upon a negative binomial model. The estimation of the overdispersion was derived from the BEAT-COPD (Biomarkers to Target Antibiotic and Systemic Corticosteroid Therapy in COPD Exacerbations) [ISRCTN92422949] data and was 1.3 with a mean exacerbation frequency of 2.85.

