#### 4. Inflammation (Weeks 0, 4, 12, 24, 36, 48)

- Cell count
  - Blood inflammatory cell differentials\*
    - WBC
    - Eosinophils
    - Neutrophils
  - Sputum inflammatory cell differentials
    - Eosinophils
    - Neutrophils
    - Macrophages
    - Lymphocytes
    - Epilthelial cells
    - Total

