# 4 General Issues for Statistical Analysis

#### 4.1 Derived/Computed Variables

**Body mass index (BMI)**: This will be derived as per WHO Guidelines, BMI measures as Kg/m^2.

Age: Age will be measured in years and will be derived from the date of birth at the randomisation date.

COPD Assessment Tool (CAT) score: The CAT consists of 8 items with scores ranging from 0 to 5 (0= no impairment). An overall score will be calculated by adding the score from each item with total scores ranging from 0 to 40, higher scores indicating a more severe health status impairment or a poorer control of COPD.

St George's Respiratory Questionnaire for COPD patients (SGRQ-C): The SGRQ-C is in two parts. Part I produces the Symptoms score, and Part 2 the Activity and Impacts scores. A Total score is then produced. Each questionnaire response has a unique empirically derived `weight'. The lowest possible weight is zero and the highest is 100. A **Total** and three component scores are calculated: **Symptoms**; **Activity**; **Impacts**.

The **Symptoms** component consists of all the questions in Part 1. The weights for Questions 1-7 are summed. A single response is required to each item. If multiple responses are given to an item, then average weight should be calculated.

The **Activity** component is calculated from the summed weights for the positive responses to items Questions 9 and 12 in Part 2 of the questionnaire.

The **Impacts** component is calculated from Questions 8, 10, 11, 13, 14 in Part 2 of the questionnaire.

Then the **Total** score is calculated by summing the weights to all the positive responses in each component.

**FEV1/FVC ratio**: FEV1 is the volume of air exhaled in 1 second, FVC is FVC is the full amount of air that can be exhaled with effort in a complete breath. FEV1/FVC ratio is a measure of airflow obstruction, with values <0.7 (70%) indicating airflow obstruction.

**BD Reversibility percentage**: this will be computed as % Reversibility = (post-BD FEV1- pre-BD FEV1) × 100/pre-BD FEV1

**RV/TLC ratio:** this is the residual volume (RV) to total lung capacity (TLC). It is calculated using  $\frac{RV}{TLC} \times 100\%$ 

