# 5.5 Secondary Outcome Analyses

### 5.5.1 Primary Analysis of Secondary Outcomes

All secondary end-points will be analysed using the modified intention-to-treat population, with the exception of adverse events, for which we will analyse the safety population, consisting of all participants who received at least one dose of trial medication.

Descriptive statistics of all the secondary outcomes listed in section 2.2 will be presented by treatment arms and overall by assessment time points (i.e by visit). Numbers (with percentages) for binary and categorical variables and means (and standard deviations), and medians (with lower and upper quartiles) for continuous variables will be presented.

All binary secondary outcomes will be compared between treatment groups using logistic regression. Odd ratio (OR) with two-side 95% CI and P-value will be reported for those outcomes.

All continuous longitudinal outcomes (repeated measurements i.e week 0, 4, 12, 24, 36 and 48) will be compared using mixed effects model with explanatory variables of treatment arm, number of exacerbations in the 12 months prior to the trial (stratification factor), visit number in weeks (categorical) and patient identification as a random effect to account for repeated measures over time. This method will able to handle missing data happening during the follow-up measurements. Adjusted mean differences alongside two sided 95% CI and P-value will be reported for these outcomes. If the distribution of the variable found to be far from normal distribution, a log transformation will be used to modify the non-normality. Adjusted geometric mean difference alongside two sided 95% CI and P-value will be reported.

To compare change from baseline to 48 weeks (pre and post treatment measurements), analysis of covariance (ANCOVA) model with baseline value as a covariate will be used. Adjusted mean differences with 95% confidence interval will be reported if the data are normally distributed. If there is severe departure from normality the first approach will be data transformation with the above technique applied to the transformed data. Adjusted geometric mean difference with 95% CI and P-value will be reported. If the data cannot be transformed to normality then the Mann-Whitney U test will be used and in this case no baseline adjustment will be made.

All safety data will be analysed as described in section 7 of this SAP.

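### The last-resort Mann-Whitney test for the baseline-to-week-48 comparison gives up the baseline covariate and yields no estimate, and the log step has no rule for values at or below zero

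*SAP*

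**What the plan says.** SAP 5.5.1 sets out two routes for continuous secondary outcomes.

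- **Longitudinal outcomes** (weeks 0 to 48) go into a mixed effects model. If the distribution is far from normal, "a log transformation will be used to modify the non-normality", and a geometric mean difference is reported. There is no further fallback.
- **Change from baseline to week 48** is analysed by ANCOVA with the baseline value as covariate. For a severe departure from normality the data are transformed and the ANCOVA repeated, again with a geometric mean result. Only if no transformation works, "then the Mann-Whitney U test will be used and in this case no baseline adjustment will be made".

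Neither route says what happens to zero or negative values. The SAP does not say whether Mann-Whitney ranks the change or the week-48 value, and it attaches no estimate or interval to that test. SAP 5.5.3 rules out sensitivity analyses for secondary outcomes.

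Three listed outcomes matter here. For BD reversibility (SAP 4.1), "this will be computed as % Reversibility", from post-BD minus pre-BD FEV1 divided by pre-BD FEV1; it is measured only at weeks 0 and 48. SAP 2.2.1 lists "Sputum inflammatory cell differentials", including eosinophils, at weeks 0 to 48. CAT (SAP 4.1) runs from 0 to 40.

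Protocol 10.6 asks for secondary outcomes as estimates with confidence intervals, without tests unless the SAP provides for them. Protocol 10.9 says that outcomes other than the primary are unadjusted in the main analyses.

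**The concern.** Non-normality is no reason to give up the baseline. Ranks of the outcome can be regressed on treatment and ranks of the baseline under similarly weak assumptions. An outcome that reaches the last step loses the precision that the baseline provides and any correction for chance imbalance. It would be reported by a p-value alone, with no planned sensitivity analysis beside it.

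The log step raises a different problem. An analyst who meets a zero has no instruction. Common software returns a missing value for the log of zero, and SAP 3.3 analyses secondary outcomes as complete cases without imputation. If zeros were lost in that way, the analysis would select on the outcome: a drug that lowers eosinophils makes more zeros in its own arm, and losing them pulls the estimate towards no effect.

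**Working it through.** **Inputs.** The documents' only power statement, "Recruitment of 80 participants with a drop-out rate of 10% will be sufficient to give 80% power at the 5% level", concerns the primary outcome, so there is no secondary-outcome figure to reproduce. It supplies the sample size: 80 × 0.90 = 72, or 36 per arm. Tests are two-sided at 5%. The documents do not give the following, so they are assumed: a treatment effect d of 0.5 SD (on the log scale for skewed data), a baseline to week-48 correlation ρ of 0.3 to 0.8, and the shape of the skewed distribution.

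**Normal data, closed form.** Power ≈ Φ(δ − 1.96), with δ = d√(n/2)/σ and 0.5 × √18 = 2.121. For ANCOVA, σ = √(1 − ρ²). For Mann-Whitney, δ is multiplied by √(3/π) = 0.977, with σ = 1 on the week-48 value and σ = √(2(1 − ρ)) on the change. At ρ = 0.7:

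- ANCOVA: 2.121/0.714 = 2.970, Φ(1.010) = 84%
- Mann-Whitney, week-48 value: 2.121 × 0.977 = 2.073, Φ(0.113) = 54.5%
- Mann-Whitney, change: 2.073/0.775 = 2.676, Φ(0.716) = 76%

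Over ρ = 0.3, 0.5, 0.7, 0.8, ANCOVA gives 60, 69, 84, 94%; Mann-Whitney on the week-48 value stays at 54.5%; on the change it gives 42, 55, 76, 91%.

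**Skewed data, simulation** (6,000 trials per setting, 36 per arm, lognormal with log-SD 1). Power in %:

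| Method | ρ 0.3 | ρ 0.5 | ρ 0.7 | ρ 0.8 |
|---|---|---|---|---|
| ANCOVA, untransformed | 40.7 | 45.0 | 57.1 | 69.4 |
| Mann-Whitney, week-48 value | 53.5 | 53.2 | 53.4 | 52.7 |
| Mann-Whitney, change | 30.5 | 40.0 | 56.7 | 73.5 |
| Rank-based ANCOVA | 57.0 | 63.9 | 78.4 | 89.9 |

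The gain of rank-based ANCOVA over Mann-Whitney on the week-48 value runs from 57.0 − 53.5 = 3.5 points to 89.9 − 52.7 = 37.2 points. With about one third zeros it runs from 51.7 − 49.2 = 2.5 to 82.8 − 50.1 = 32.7. Rank-based ANCOVA also beats Mann-Whitney on the change at every ρ in both skewed settings. Type I error was about 4 to 6% for every method.

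**Values at or below zero.** BD reversibility % is zero when post-BD and pre-BD FEV1 are equal, and negative when post-BD is lower. CAT has eight items scored from 0, so its minimum is 8 × 0 = 0. A sputum differential can contain no eosinophils. A plain log is undefined for all of these.

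**If zeros were dropped.** Assume 20% zeros on placebo, so the cut lies at z = −0.842. A 0.5 SD reduction moves it to −0.842 + 0.5 = −0.342, and Φ(−0.342) = 37% zeros on active. In 3,000 simulated trials per setting, at ρ = 0.4, 0.6, 0.7, 0.8:

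- ANCOVA on the log with zeros dropped: power 26, 36, 48, 66%
- ANCOVA on log(x+c) with zeros kept: power 57, 66, 75, 85%

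Dropping kept only 61 to 67% of participants and shrank a true log effect of −0.50 to between −0.29 and −0.38. These runs are of a baseline-to-week-48 ANCOVA. For sputum counts in the mixed model they show the direction of the bias, not its size.

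**The case against.** The fallback is narrow. Mann-Whitney comes third, after ANCOVA and transformation, and only in the week-48 comparison. A reader might infer that all skewed secondary outcomes end there; they do not. Sputum counts mainly follow the mixed-model route, which has no Mann-Whitney step. BD reversibility % does belong to the week-48 route, but the trigger is severe non-normality, not negative values, which an untransformed ANCOVA accepts. All of this stands.

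A reader might infer that the baseline is thrown away entirely. The documents establish only that the covariate is dropped. If the change is ranked, the baseline still enters, and the SAP does not say which is ranked.

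A reader might infer that power is lost precisely where data are skewed. That is false as a general statement: at ρ = 0.3 and 0.5 Mann-Whitney on the week-48 value beats untransformed ANCOVA under strong skew (53.5 against 40.7%, 53.2 against 45.0%). The loss is relative to a baseline-adjusted rank or suitable log analysis, and it grows with ρ.

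A reader might infer that the SAP plans to delete zeros. It does not. An observed zero is not missing data, and deletion would be an artefact of software. The fault is the absence of a rule.

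Finally, an unadjusted last resort does not conflict with Protocol 10.9, which makes other outcomes unadjusted; it is the SAP's ANCOVA that departs from that section. What remains is that the SAP chose baseline adjustment, gives it up without need at the last step, and leaves that step without the estimate and interval that Protocol 10.6 asks for.

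**Conclusion.** The point holds in limited form. For the baseline-to-week-48 comparison, the last-resort test is valid but less efficient than a baseline-adjusted rank analysis of the same data, by about 3 to 37 points of power against ranking the week-48 value. That range rests on 36 per arm, a 0.5 SD effect, lognormal shapes and correlations of 0.3 to 0.8, none of the last three given in the documents. At a correlation of 0.3 the gain is negligible. The actual number with week-48 spirometry may be below 36 per arm, because the schedule of procedures suspended those assessments during COVID-19 restrictions.

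That the test comes without an estimate and interval, that the ranked quantity is not stated, and that values at or below zero have no rule are gaps in the text and need no assumption. The bias towards no effect is conditional on zeros being dropped; its size rests on the assumed 20% of zeros. The primary analysis is unaffected and no stated power target is breached.

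**What to change.** In SAP 5.5.1:

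1. Replace the Mann-Whitney fallback with rank-based ANCOVA: the ranked week-48 value on treatment, ranked baseline and the stratification factor. Report an effect estimate with its 95% confidence interval alongside, for example a baseline-adjusted median difference.
2. For outcomes that can be zero, state that observed zeros are kept, and give a rule for log(x+c), such as c equal to half the smallest non-zero value pooled over both arms. This is a rule applied to the data, not a constant known in advance. Report the result as a ratio for x+c, because it does not back-transform to a ratio for x.
3. For BD reversibility %, use untransformed or rank-based ANCOVA, not a log. An offset chosen for zeros does not help with negative values.

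The work is wording and standard software. There are two costs. A rank model gives a less direct effect size, hence the accompanying estimate. And the revision history shows that SAP 3.0 followed database lock and review of the draft statistical report, so the change has to be recorded and justified under SAP 6.2 as post-lock, with the results of the existing rule shown beside it for any outcome where that rule was used.

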### 5.5.2 Secondary analysis of the Secondary outcome

Per-protocol population analysis will be carried out for key secondary outcomes. These are FEV1 post-bronchodilator, SGRQ-C and CAT. All other methods regarding the model construction and presentation will remain the same.

# 5.5.3 Sensitivity Analyses

There will be no sensitivity analyses carried out for any secondary outcome measures.

# 6 Exploratory Outcome Analyses

The accumulation of the exploratory outcome data will take several months following completion of the week 60 follow-up period. Therefore the exploratory outcome analyses will not form part of initial data lock and analysis of this data will occur after the primary and secondary outcomes have been completed and reported. All exploratory end-points will be analysed at a later stage outside the remit of Leicester CTU. Therefore those analyses may not bound by this SAP, though they are expected to follow the broad principles laid out within this document.

# 6.1 Subgroup Analyses

A subgroup analysis of the primary outcome will be carried out based on baseline blood eosinophil, dichotomised by the median value. The primary outcome of COPD exacerbations in 48 weeks will be summarised by low or high eosinophil count and analysed as described in section 5.4.1. An indicator variable to specify the eosinophil group (low or high) will be added to the analysis model. The additional of an interaction term between eosinophil indicator variable and treatment group will assess the difference in treatment efficacy between low and high eosinophil groups. *Post hoc* the clinically important eosinophil cut-off (>300 eosinophils/ $\mu$ L) was included as an additional subgroup analysis.

Additional subgroup analyses of the SGRQ-C and FEV1 will also be carried out based on the baseline blood eosinophil, dichotomised by the median value. The SGRQ-C sore and FEV1 will be summarised by low or high eosinophil count and analysed as described in section 5.4.1. An indicator variable to specify the eosinophil group (low or high) will be added to the analysis model. The addition of an interaction term between eosinophil indicator variable and treatment group will assess the difference in SGRQ-C score and FEV1 between the low and high eosinophil groups.

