10.8 Subgroup analyses

The Statistical analysis plan will include a planned sub-group analysis based on baseline blood eosinophil count as described in section 3.4.

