### 2.4 Subgroups and/or interactions

There will be a subgroup analysis of the primary outcome, rate of protocol-defined moderate to severe COPD exacerbations through 48 weeks treatment period and secondary outcomes SGRQ-C and FEV1 by baseline blood eosinophil count (dichotomised about median value).

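### The eosinophil subgroup question is tested only through binary cuts; a continuous log-eosinophil interaction should be added, for a modest and conditional gain

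*SAP*

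**What the plan says.** Baseline blood eosinophil count is the only planned subgroup factor. Protocol 10.8 says "The Statistical analysis plan will include a planned sub-group analysis based on baseline blood eosinophil count" and refers to Protocol 3.4. Neither section gives a cut-off or a functional form.

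The SAP supplies the form. Section 2.4 analyses exacerbations, SGRQ-C and FEV1 "by baseline blood eosinophil count (dichotomised about median value"). Section 1.1.4 fixes the same split. Section 6.1 says of exacerbations: "A subgroup analysis of the primary outcome will be carried out based on baseline blood eosinophil, dichotomised by the median value". It repeats the split for SGRQ-C and FEV1, which "will also be carried out based on the baseline blood eosinophil, dichotomised by the median value". In 6.1 a low/high indicator enters the model, and the "interaction term between eosinophil indicator variable and treatment group will assess the difference in treatment efficacy between low and high eosinophil groups".

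Section 6.1 also reports, as post hoc, a second binary analysis at "the clinically important eosinophil cut-off" of more than 300 cells/µL. The revision history dates this to version 2.1, after database lock and review of the draft statistical report. No continuous eosinophil term, transformation or spline appears anywhere.

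The count itself is available: a full blood count is taken at screening, and SAP Table 4 summarises baseline eosinophils as a mean with SD.

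**The concern.** A median split treats patients just either side of the cut as opposites and patients far apart on the same side as identical. If the treatment effect changes gradually with the count, that discards information from an interaction test that has little to spare, because the trial was sized for the overall comparison. The value of a sample median is also known only once the data are in, and it does not carry over to another population.

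The biological rationale in Protocol section 1 links IL-33 to eosinophil recruitment, and eosinophilic inflammation to exacerbations. Whether benefit depends on eosinophils is therefore a central secondary question. As planned, the answer comes from two binary cuts, one of them chosen after lock. A single continuous model would give the estimated effect at any count, including 300.

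**Working it through.** **1. The plan's own figure.** Neither document states power or precision for the subgroup analysis. The only power figure is for the overall comparison: 80 randomised, 10% drop-out, 80% power, two-sided 5%. Whether that figure can be reproduced is a separate matter, and nothing below rests on it.

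**2. Inputs from the documents.** 80 × 0.9 = 72 evaluable, or 36 per arm; 1:1 allocation; 48 weeks; placebo rate 2 or 2.5 per year (midpoint 2.25); over-dispersion 1.3. SAP 5.4.1 equates a dispersion of zero with the Poisson model, so 1.3 is read here as the negative binomial parameter.

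**3. Assumptions, not in the documents.** The eosinophil distribution, the shape of effect modification and its size.

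**4. Relative efficiency.** For an interaction test, the information kept is approximately the squared correlation between the analysed form and the true modifier. For a standard normal X split at its median, the correlation is E|X| = √(2/π) = 0.798, and its square is 2/π = 0.637. The loss is 1 − 0.637 = 36%. Then 72 × 0.637 ≈ 46 patients' worth of information, or 80 × 0.637 ≈ 51 without drop-out. Other shapes give other answers:

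| True effect modification | Median split keeps | Continuous term keeps |
|---|---|---|
| Linear in log count, log count normal | 0.64 | 1.00 |
| Linear, covariate uniform | 0.75 | 1.00 |
| Linear in raw count, log-SD 0.5 | 0.52 | 0.88 (log term) |
| Linear in raw count, log-SD 0.7 | 0.42 | 0.77 (log term) |
| Linear in raw count, log-SD 0.9 | 0.32 | 0.65 (log term) |
| Step at the median | 1.00 | 0.64 |
| Step 0.25 SD above the median | 0.67 | 0.62 |
| Step at the 75th percentile | 0.33 | 0.54 |

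**5. Simulated power for exacerbations.** Negative binomial counts, 36 per arm, placebo rate 2.25 per year, two-sided 5%. The interaction is the change in log rate ratio per SD of log eosinophils.

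| Scenario | Continuous | Median split |
|---|---|---|
| Dispersion 1.3, 0.7 per SD | 51–53% | 39–43% |
| Dispersion 1.3, 0.35 per SD | 18% | 15% |
| Dispersion 1/1.3 = 0.77, 0.7 per SD | 66% | 52% |
| Dispersion 0.77, 0.35 per SD | 22% | 17% |
| Dispersion 1.3, threefold step in rate ratio at the median | 27% | 32% |
| Dispersion 1.3, step at the 75th percentile | 16% | 11% |

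The ranges come from separate runs. One further run of the first scenario gave 49% against 38%. At 1,500 trials the simulation error near 50% is about √(0.25/1500) = 1.3 points. A second run with a step at the median gave 27% against 38%. With 40 per arm and dispersion 1.3, power at 0.7 per SD was 55% against 45%. With no interaction, rejection at 36 per arm and dispersion 1.3 was 6.5% (continuous) and 5.9% (split), both near nominal.

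Efficiency from simulation is the squared ratio of mean z-statistics. For example, at 36 per arm, dispersion 1.3 and 0.7 per SD it is (1.638/1.913)² = 0.73. Over the log-linear settings it ran from about 0.64 to 0.74.

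**6. Size of the assumed interactions.** From −1 to +1 SD, 0.7 per SD changes the rate ratio by exp(1.4) = 4.06-fold, and 0.35 per SD by exp(0.7) = 2.01-fold. Both are large.

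**The case against.** The SAP already does much that is right: one subgroup factor, a cut rule that is not tuned to outcome, a formal interaction test, and open labelling of the 300 cut as post hoc. Protocol 3.4 asks for effects in subgroups defined by eosinophil count, which a split answers directly. The log-linear simulations generate data from the model they favour, and when the truth is a step at or close to the median the split does as well or better. At a twofold change across ±1 SD the gain is only about 3 points of power. All of this stands. It limits the gain but does not remove it, since the documents give no reason to expect a step at this sample's median.

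A reader might infer three stronger things that the documents do not support:

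- **That a third of the information is lost outright.** The 36% figure depends on normality and log-linearity. For the linear shapes in the table the split's loss runs from 25% to 68%, and for a step at the median the comparison reverses.
- **That the 300 cut was added because the median split was found wanting, or that the split led to it.** The revision history says only that a clinically important cut was added alongside the median. It names no fault in the median, and a continuous analysis would not have ruled out a later request for a clinical threshold.
- **That the continuous test should now replace the median split.** SAP 3.0 was signed after lock and review of the draft report. Demoting the prespecified test at that point would be a results-aware change.

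**Conclusion.** The point holds as a worthwhile improvement to a supportive analysis, and it does not touch the primary comparison. The eosinophil question is tested only through binary cuts although the continuous count is in hand. Under approximate normality and log-linear effect modification, the split keeps about 0.64 to 0.74 of the interaction information. In the simulated settings at 36 per arm that is about 3 to 14 points of power, depending on the interaction size and dispersion assumed. Neither test is adequately powered at this sample size, so a non-significant interaction from either should not be read as absence of effect modification. The power figures are for exacerbations only; the 2/π argument carries over to SGRQ-C and FEV1 under the same assumptions, but no power was simulated for them.

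**What to change.** In SAP 1.1.4, 2.4 and 6.1, add a treatment-by-continuous log-eosinophil interaction for exacerbations, SGRQ-C and FEV1. Report the interaction estimate with its 95% CI, and plot the treatment effect with 95% CI across the observed eosinophil range. State how any zero counts are handled before taking logs.

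Keep and report the prespecified median-split interaction, and keep the 300 cut with its post hoc label. Label the continuous analysis post hoc and justify it under SAP 6.2. The SAP introduction already allows post hoc analyses that are identified as such in the study report. In a plan still to be unblinded, the continuous interaction would be the main subgroup test, with the splits as supporting display.

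The cost is a few lines of SAP text, one extra model and one plot per outcome. No new data are needed, and the protocol wording does not have to change. The downside is the log-linearity assumption. A non-linear term can be added as a check, but 72 to 80 patients can test it only weakly, so the plot and the split should be shown beside the model.

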# 5.4 Primary Outcome Analysis

#### 5.4.1 Primary Analysis of Primary Outcome

The main approach to primary analyses will be an intention-to-treat (ITT), where the ITT population consist of all randomised participants into the trial (regardless of whether they received trial drug). Descriptive statistics of the estimated exacerbations rates in the 48 week treatment period will be presented by treatment arm and overall (Table 5 in Appendix-1). Histogram of the number of exacerbations in the 48 week period by patient will be drawn to check the distribution of the number of exacerbations during treatment (Figure 5). Cumulative number of exacerbations will be plotted by treatment arm (Figure 6).

A generalised linear model (assuming a negative binomial distribution, which accounts for variability among patients in the number of and frequency of exacerbation) will be fitted for the primary outcome of COPD exacerbations during the 48 week treatment period as an outcome with explanatory variables of treatment arm and number of exacerbation in the 12 months prior to the trial (stratification factor), and log-time on study as an offset. The offset (log-time), allows for different lengths of time on treatment for each participant [2]. This assumes that missing data is missing at random (MAR), and will be applied where all of the available observed data are analysed without deletion nor imputation.

The primary outcome data is assumed to follow a negative binomial distribution with the over dispersion estimated to be 1.3. The primary analysis of the primary outcome will give an estimate of the significance of the dispersion parameter. If the dispersion is found to be non-significant (i.e no evidence of over-dispersion) we will consider the simpler Poisson model where the dispersion parameter equals to zero. The ratio of the exacerbation rates (RR) on the anti-ST2 relative to the placebo, associated two-sided 95% confidence interval (CI) and p-value will be reported (Table 5 in Appendix-1). A value of 1.0 would indicate the same rate as placebo; the lower the ratio the greater reduction in exacerbations compared with placebo. A two-sided p-value  $\leq 0.05$  will be considered as a significant difference in the number of COPD exacerbations in 48 weeks between the two treatment arms.

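### SAP 6.1 refers the SGRQ-C and FEV1 eosinophil subgroup analyses to section 5.4.1, the exacerbation-count model, which is not valid for continuous outcomes; the reference and the details that depend on it need correcting

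*SAP*

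**What the plan says.** SAP 1.1.4 and 2.4 name three outcomes to be compared by baseline blood eosinophil group, split at the median: exacerbation rate, SGRQ-C and FEV1. Protocol 3.4 names the same three.

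SAP 6.1 has one paragraph for exacerbations and one for the other two outcomes. The second says: "The SGRQ-C sore and FEV 1 will be summarised by low or high eosinophil count and analysed as described in section 5.4.1". It then adds an eosinophil indicator and a treatment-by-eosinophil interaction, which "will assess the difference in SGRQ-C score and FEV1 between the low and high eosinophil groups".

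Section 5.4.1 specifies "A generalised linear model (assuming a negative binomial distribution", and this model "will be fitted for the primary outcome of COPD exacerbations during the 48 week treatment period as an outcome". Its covariates are treatment arm and prior exacerbations, "and log-time on study as an offset". Poisson is the fallback if over-dispersion is not significant. The result is a rate ratio in the ITT population.

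The models for continuous secondary outcomes are in 5.5.1, in the modified ITT population. Repeated measurements go to a mixed effects model. For change from baseline to week 48, an "analysis of covariance (ANCOVA) model with baseline value as a covariate will be used".

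**The concern.** Section 5.4.1 offers no model for a continuous outcome and no place for the outcome's baseline value. Nothing in SAP 2.4, SAP 6.2 or Protocol 10.8 overrides the reference to it. An analyst who follows SAP 6.1 literally cannot produce a valid analysis for two of the three subgroup outcomes.

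An analyst who recognises the slip still has to choose what was meant, because 5.5.1 contains two models and a different population, and 6.1 does not say which FEV1 is used. The SAP revision history places version 2.1 after database lock and review of the draft report, with version 3.0 as its sign-off. A choice made now would therefore be made with the data available.

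The interaction sentence has a separate fault. A treatment-by-eosinophil term measures how the treatment effect differs between eosinophil groups, not how the score or the FEV1 differs between them. The exacerbation paragraph of 6.1 puts this correctly.

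**Working it through.** The documents give no figure to reproduce. The first step compares the sections, and the second illustrates the size under assumed values.

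**1. The two sections compared**

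| Feature | SAP 5.4.1 | SAP 5.5.1 |
|---|---|---|
| Outcome | Event count | Continuous secondary outcomes |
| Model | Negative binomial or Poisson, offset log time | Mixed model, or ANCOVA |
| Outcome's baseline value | Absent | Covariate in the ANCOVA |
| Effect measure | Rate ratio | Adjusted mean difference |
| Population | ITT | Modified ITT |

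SAP 4.1 describes SGRQ-C as a weighted score, and SAP 1.1.4 asks for its change. A change can be negative, and a negative binomial model has no support below zero. In one simulated data set with assumed values (72 patients, 61% of changes negative), the fit failed.

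**2. FEV1 interaction standard error**

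Assumed, not from the documents: mean 1.3 L, SD 0.5 L, baseline to week-48 correlation 0.85, and a true interaction of 0.15 L. The planned 80 patients are split equally, 20 in each of four treatment-by-eosinophil cells, with constant follow-up.

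- ANCOVA: SE = SD × √(1 − r²) × √(4/20) = 0.5 × √(1 − 0.7225) × 0.447 = 0.118 L.
- Linear model without baseline: 0.5 × 0.447 = 0.224 L.
- Count model: the variance is μ + kμ², so SE on the log scale = √[4 × (1/μ + k)/20]. Matching moments, k = (SD² − μ)/μ², with a floor of zero.
 - In litres, the variance 0.25 is below the mean 1.3, so k = 0 (Poisson). SE = √(4/26) = 0.39, and 0.39 × 1.3 = 0.51 L. Ratio to ANCOVA: 0.51/0.118 = 4.3.
 - In millilitres, k = (250,000 − 1,300)/1,690,000 = 0.147. SE = √[4 × (0.00077 + 0.147)/20] = 0.172, and 0.172 × 1.3 = 0.224 L. Ratio: 0.224/0.118 = 1.9.

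The same data therefore give different inference in litres and in millilitres. In millilitres the SE equals that of the linear model without baseline, so on this calculation the loss comes almost entirely from dropping the baseline value.

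**3. ANCOVA power for the same interaction**

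0.15/0.118 = 1.27, and Φ(1.27 − 1.96) = Φ(−0.69), or about 0.25. A simulation under the same assumptions gave 0.24.

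**4. SGRQ-C as an absolute score**

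Assumed: mean 50, SD 17, correlation 0.7, 20 per cell.

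- Count model: k = (289 − 50)/2,500 = 0.096. SE = 50 × √[4 × (0.02 + 0.096)/20] = 7.6 points.
- ANCOVA: 17 × 0.447 × √(1 − 0.49) = 5.4 points. Ratio: 1.4.

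**5. The offset**

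With week-48 visits inside the ±7-day window, log time ranges over log(49/47) = 0.04, so the offset is almost constant.

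**The case against.** The strongest reply is that this is a misdirected section number, not a choice of model. The second paragraph of 6.1 repeats the first almost word for word, section number included. It goes on to speak of a difference in score and FEV1, not a rate ratio. SAP 2.4 calls both outcomes secondary, and 5.5.1 covers all secondary endpoints. A competent analyst would probably not fit a count model. This stands, and it lowers the severity. It does not remove the point, because the intended analysis cannot be recovered from the text:

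- **Model.** SAP 2.2.1 lists lung function at weeks 0 and 48, which suggests ANCOVA. The visit schedule has post-bronchodilator spirometry at weeks 4, 12, 24, 36 and 48, which suggests the mixed model.
- **Data.** Under the COVID-19 footnote, week-48 SGRQ-C and spirometry were not done during restrictions. A week-48 analysis drops those participants, whereas a mixed model keeps their earlier visits. The choice could change the result.

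A reader might infer more than the documents support:

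- **A fourfold loss and no power.** These follow only with FEV1 in litres, and the SAP gives no analysis unit. In millilitres the ratio is 1.9.
- **A real lung-function effect hidden by this error.** Under the same assumptions the ANCOVA itself has only about 24% power.
- **FEV1 inflated by short follow-up,** such as 1.3 L at 24 weeks read as 2.6 L per 48 weeks. A participant followed for 24 weeks would normally have no week-48 FEV1, and among those who do the offset is nearly constant.

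**Conclusion.** The point holds as an error in the written plan, most likely a copied cross-reference. Section 5.4.1 is not a valid model for change in SGRQ-C or for FEV1. The conclusion rests on the text and on the support and variance of a count model, not on the simulated or assumed figures.

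The size is illustrative. For FEV1 the interaction SE is about 1.9 to 4 times the ANCOVA value, depending on the unit, under the assumed mean, SD, correlation and cell size.

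It would be wrong to conclude that a count model was or would be fitted to FEV1, or that the trial's main results are in doubt. The primary analysis, the exacerbation subgroup analysis and the main secondary analyses each have their own specification and are unaffected. Severity: should fix.

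**What to change.** In the second paragraph of SAP 6.1:

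1. Replace the reference to 5.4.1 with 5.5.1.
2. For each outcome, use the same 5.5.1 model and modified ITT population as its main secondary analysis, adding eosinophil group and the treatment-by-eosinophil term. Tying the choice to the main analysis avoids a fresh choice after lock.
3. State which model that is for SGRQ-C and which for FEV1.
4. State that FEV1 is post-bronchodilator, the FEV1 that 5.5.2 names as key.
5. State the time point of the interaction. The mixed model in 5.5.1 lists no treatment-by-visit term, so the added interaction would otherwise be an average over visits.
6. Describe the interaction as the difference in treatment effect between eosinophil groups.

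Record the correction and its reason under SAP 6.2, because version 3.0 was signed after database lock. The cost is a short SAP wording change and an entry in the statistical report. No new data are needed. If these subgroup analyses have already been run, the report should state which model was used.
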